2.2.3 Pharmacokinetics and Drug Metabolism

Clinical pharmacokinetics studies have shown that thalidomide when administered as a single 200-mg dose, the mean peak plasma concentration is 1.9 $\mu\text{g/ml} \pm 0.5$, occurring 3.3 hours ± 1.7 after dosing. Mean half-life of elimination is 5.9 hours ± 2.1 . Single dose, dose proportionality was evaluated over the clinical dose range, i.e., from 50 to 400 mg. The extent of absorption is proportional to dose, however, as the dose increases beyond 200 mg, a flattening of the peak concentration is seen with a delay in the time to the peak concentration. The mean peak plasma concentration following a single 400 mg dose administration was 2.82 $\mu\text{g/ml} \pm 0.80$ occurring by 4.3 ± 1.6 hours after the dose; mean half-life of elimination was 7.29 hours ± 2.62 . The rate of absorption was also slower at the highest dose as evidenced by a rate constant of absorption that was approximately one-half that observed at the lower doses.

Distribution

In human blood plasma, the geometric mean plasma protein binding was 55% and 66%, respectively, for (+)-(R)- and (-)-(S)-thalidomide.⁸

Metabolism

At the present time, the exact metabolic route and fate of thalidomide is not known in humans. Thalidomide itself does not appear to be hepatically metabolized to any large extent, but appears to undergo non-enzymatic hydrolysis in plasma to multiple metabolites. In a repeat dose study in which THALOMID® (thalidomide) 200 mg was administered to 10 healthy females for 18 days, thalidomide displayed similar pharmacokinetic profiles on the first and last day of dosing.

Elimination

The mean half-life of elimination ranges from approximately 5 to 7 hours following a single dose and is not altered upon multiple dosing. As noted in the metabolism subsection, the precise metabolic fate and route of elimination of thalidomide in humans is not known at this time. Thalidomide itself has a renal clearance of 1.15 mL/minute with less than 0.7% of the dose excreted in the urine as unchanged drug. Following a single dose, urinary levels of thalidomide were undetectable 48 hrs after dosing. Although thalidomide is thought to be hydrolyzed to a number of metabolites, only a very small amount (0.02% of the administered dose) of 4-OH-thalidomide was identified in the urine of subjects 12 to 24 hours after dosing.

Supplied

Thalidomide is commercially available. Patients, prescribers and dispensing pharmacies must be registered in the FDA-mandated S.T.E.P.S.® program. Celgene will provide Thalomid® (thalidomide) study participants at no charge through the Protocol Therapy Assistance Program (P-TAP).

Prescribing Information

Thalidomide (Thalomid®) will be provided in accordance with the S.T.E.P.S.® program. All physicians who prescribe thalidomide for research subjects enrolled into this trial and all research subjects enrolled into this trial must be registered in and must comply with all requirements of the S.T.E.P.S.® program of Celgene Corporation. Only enough thalidomide for 28 days can be prescribed at one time. Prescriptions must be filled within 7 days.

Dosage form

[figure not shown]
Thalidomide will be supplied as capsules for oral administration.

2.2 Lenalidomide

2.2.1 Description of Lenalidomide

REVLIMID® (lenalidomide), a thalidomide analogue, is an immunomodulatory agent with anti-angiogenic properties. The chemical name is 3-(4-amino-1-oxo 1,3-dihydro -2*H*-isoindol-2-yl) piperidine-2,6-dione and it has the following chemical structure:

- *Chemical Structure of Lenalidomide*

3-(4-amino-1-oxo 1,3-dihydro-2*H*-isoindol-2-yl) piperidine-2,6-dione

The empirical formula for lenalidomide is C₁₃H₁₃N₃O₃, and the gram molecular weight is 259.3.

Lenalidomide is an off-white to pale-yellow solid powder. It is soluble in organic solvent/water mixtures, and buffered aqueous solvents. Lenalidomide is more soluble in organic solvents and low pH solutions. Solubility was significantly lower in less acidic buffers, ranging from about 0.4 to 0.5 mg/ml. Lenalidomide has an asymmetric carbon atom and can exist as the optically active forms S(-) and R(+), and is produced as a racemic mixture with a net optical rotation of zero.

2.2.2 Clinical Pharmacology

Mechanism of Action:

The mechanism of action of lenalidomide remains to be fully characterized. Lenalidomide possesses immunomodulatory and antiangiogenic properties. Lenalidomide inhibited the secretion of pro-inflammatory cytokines and increased the secretion of anti-inflammatory cytokines from peripheral blood mononuclear cells. Lenalidomide inhibited cell proliferation with varying effectiveness (IC₅₀s) in some but not all cell lines. Of cell lines tested, lenalidomide was effective in inhibiting growth of Namalwa cells (a human B cell lymphoma cell line with a deletion of one chromosome 5) but was much less effective in inhibiting growth of KG-1 cells (human myeloblastic cell line, also with a deletion of one chromosome 5) and other cell lines without chromosome 5 deletions. Lenalidomide inhibited the expression of cyclooxygenase-2 (COX-2) but not COX-1 in vitro.

2.2.3 Pharmacokinetics and Drug Metabolism:

Absorption

Lenalidomide, in healthy volunteers, is rapidly absorbed following oral administration with maximum plasma concentrations occurring between 0.625 and 1.5 hours post-dose. Co-administration with food does not alter the extent of absorption (AUC) but does reduce the maximal plasma concentration (C_{max}) by 36%. The pharmacokinetic disposition of lenalidomide is linear. C_{max} and AUC increase proportionately with increases in dose. Multiple dosing at the recommended dose-regimen does not result in drug accumulation.

Pharmacokinetic sampling in myelodysplastic syndrome (MDS) patients was not performed. In multiple myeloma patients maximum plasma concentrations occurred between 0.5 and 4.0 hours post-dose both on Days 1 and 28. AUC and C_{max} values increase proportionally with dose following single and multiple doses. Exposure (AUC) in multiple myeloma patients is 57% higher than in healthy male volunteers.

Pharmacokinetic Parameters

Distribution:

In vitro (¹⁴C)-lenalidomide binding to plasma proteins is approximately 30%.

Metabolism and Excretion:

The metabolic profile of lenalidomide in humans has not been studied. In healthy volunteers, approximately two-thirds of lenalidomide is eliminated unchanged through urinary excretion. The process exceeds the glomerular filtration rate and therefore is partially or entirely active. Half-life of elimination is approximately 3 hours.

Supplier(s)

Celgene Corporation will supply Revlimid® (lenalidomide) to study participants at no charge through the RevAssist® program. All physicians who prescribe lenalidomide for research subjects enrolled into this trial and all research subjects enrolled into this trial must be registered in and must comply with all requirements of Celgene's RevAssist® program.

Dosage form

Lenalidomide will be supplied as capsules for oral administration.

Packaging

Lenalidomide will be shipped directly to patients. Bottles will contain a sufficient number of capsules for one cycle of dosing.

Storage

Lenalidomide should be stored at room temperature away from direct sunlight and protected from excessive heat and cold.

Prescribing Information

Lenalidomide (Revlimid®) will be provided to research subjects for the duration of their participation in this trial at no charge to them or their insurance providers. Lenalidomide will be provided in accordance with the RevAssist® program. Per standard RevAssist® requirements all physicians who prescribe lenalidomide for research subjects enrolled into this trial, and all research subjects enrolled into this trial, must be registered in and must comply with all requirements of Celgene's RevAssist® program. Prescriptions must be filled within 7 days. Only enough lenalidomide for one cycle of therapy will be supplied to the patient each cycle.

2.3 Dexamethasone

2.3.1 Description of Dexamethasone

Dexamethasone is a potent synthetic glucocorticoid that affects almost every body system. It has anti-inflammatory, immunosuppressant, antineoplastic and antiemetic properties. Dexamethasone is well established in the treatment of myeloma and is part of many, usually pulsed, regimens. Alexanian et al.(30) treated 112 newly diagnosed, chemo naïve myeloma patients with dexamethasone. Using criteria based on a 75% or greater reduction of calculated tumor mass, the overall response rates were approximately 43%.

2.3.2 Mechanism of Action:

The mechanism of control with dexamethasone remains unclear. As an antineoplastic agent, it may bind to specific protein (receptors) within the cell forming a steroid-receptor complex. Binding of the receptor-steroid complex with nuclear chromatin alters message RNA (mRNA) and protein synthesis within the cell. It also inhibits the expression of interleukin- 6 (IL-6) in myeloma cells, a growth factor considered to be a major mediator of plasma cell proliferation. In view of the probably dominant role of bone marrow stromal cells in the production of IL-6, dexamethasone may induce a plasma cell apoptosis by blocking the IL-6 support network.

2.3.3 Adverse events:

The common side effects related to dexamethasone include: nausea, vomiting, hyperphagia, weight gain, gastrointestinal bleeding or ulcer, euphoria, headache, psychosis, depression, seizures, muscle weakness, insomnia, thrombophlebitis, menstrual irregularities, infection, cataracts or glaucoma, osteoporosis, fluid and electrolyte disturbances, edema, hypertension, hyperglycemia, thrush, pancreatitis, ecchymosis, acne, delayed wound healing and rash.

2.3.4 Distribution:

Dexamethasone is manufactured by several pharmaceutical companies and the use of any generic dexamethasone is acceptable in this study. Since package inserts are periodically updated to reflect more current safety and other information, please refer to the FDA website: www.accessdata.fda.gov/scripts/cder/dregsafda for the most recent version.

3.0 Rationale

Multiple myeloma (MM) is an incurable disease that is characterized by the proliferation of clonal plasma cells in the bone marrow. Conventional chemotherapy and autologous stem cell transplantation have improved survival. However, because MM remains an incurable disease, innovative approaches are needed. The immunomodulatory drug thalidomide and the combination of thalidomide/dexamethasone have been approved for both relapsed/refractory disease and front line MM therapy. Lenalidomide is an immunomodulatory derivative that has demonstrated significant activity with acceptable toxicity in patients with refractory and relapsed MM. Lenalidomide has demonstrated activity in patients who have both responded to prior thalidomide as well as patients who are refractory to prior thalidomide, suggesting a different mechanism of action for the immunomodulatory drugs.

However despite the recent advancements in MM with several new agents recently approved, including bortezomib, lenalidomide and pegylated doxorubicin, the disease remains incurable and attempts to increase the response rates in the relapsed/refractory setting are warranted. The aim of this study is to evaluate in a phase I/II clinical trial the safety, tolerability, and efficacy of the combination of lenalidomide, thalidomide and dexamethasone in relapsed or refractory MM patients.

4.0 Objectives

Phase 1:

Primary Objectives

1. To determine the maximum tolerated dose (MTD) of the combination of lenalidomide and thalidomide and dexamethasone (LTD) in patients with relapsed/refractory multiple myeloma (RRMM).

Secondary Objectives

1. To determine the Overall response rate (ORR)
2. To determine the Time to progression (TTP)
3. To determine the Progression free survival (PFS)
4. To determine the Time to best response

Phase 2:

Primary objective:

1. To determine the overall (CR + VGPR+ PR) response rate of the combination after 4 cycles of therapy.

Secondary Objectives

1. To determine the CR, VGPR
2. To determine the Time to progression (TTP)
3. To determine the Progression free survival (PFS)
4. To determine the Time to best response
5. To assess the safety of the combination of LTD in patients with RRMM.
6. Time to next therapy
7. Symptom measurement - Multiple-symptom assessment tool

5.1 **Selection of Patients**

5.2 **Inclusion Criteria**

1. Understand and voluntarily sign an informed consent form.
2. Age \geq 18 years at the time of signing the informed consent form.
3. Relapsed/refractory MMM with measurable levels of myeloma paraprotein in serum (\geq 0.5 g/dl), urine (\geq 0.2 g excreted in a 24-hour collection sample), or abnormal free light chain (FLC) ratio.
4. Serum Creatinine \leq 2.5 mg/dl
5. Females of childbearing potential (FCBP)[†] must have a negative serum or urine pregnancy test with a sensitivity of at least 50 mIU/mL within 10-14 days prior to and again within 24 hours of starting lenalidomide and must either commit to continued abstinence from heterosexual intercourse or begin TWO acceptable methods of birth control, one highly effective method and one additional affective method AT THE SAME TIME, at least 28 days before she starts taking lenalidomide. FCBP must also agree to ongoing pregnancy testing. Men must agree to use a latex condom during sexual contact with a female of childbearing potential even if they have had a successful vasectomy. All patients must be counseled at a minimum of every 28 days about pregnancy precautions and risks of fetal exposure. See Appendix A: risks of Fetal Exposure, Pregnancy Testing Guidelines and Acceptable Birth Control methods.

[†] A female of childbearing potential is a sexually mature woman who: 1) has not undergone a hysterectomy or bilateral oophorectomy; or 2) has not been naturally postmenopausal for at least 24 consecutive months (i.e., has had menses at any time in the preceding 24 consecutive months).

6. Laboratory test results within these ranges:
Absolute neutrophil count $>$ 1000 cells/mm³
Platelet count $>$ 50,000 cells/mm³ for patients with $<$ 50% of bone marrow plasma cells and platelet count $>$ 25,000 cells/mm³ for patients in whom $>$ 50% of the bone marrow nucleated cells were plasma cells
Total bilirubin \leq 2.0 mg/dL
AST (SGOT) and ALT (AGPT) $<$ 3 x ULN
7. Able to take prophylactic anticoagulation, warfarin or equivalent agent.
8. Patient is able to understand and comply with the terms and conditions of the Lenalidomide and Thalidomide Counseling Program.
9. All study participants must be registered into the mandatory RevAssist® program, and be willing and able to comply with the requirements of RevAssist®, AND the S.T.E.P.S.® program.

5.3 **Exclusion Criteria**

1. Any serious medical condition, or psychiatric illness that would prevent the subject from signing the informed consent form.
2. Pregnant or breast feeding females. (Lactating females must agree not to breast feed while taking lenalidomide).
3. Use of any cancer therapy within 21 days prior to beginning cycle 1 day 1 of therapy (radiation therapy allowed within 5 days of completion of radiation therapy).
4. Known hypersensitivity to thalidomide, lenalidomide and dexamethasone.
5. The development of erythema nodosum if characterized by a desquamating rash while taking thalidomide or similar drugs.

6.1 Treatment Plan

This is an open-label, phase I/II, single center study, which will enroll up to 54-64 patients with relapsed/refractory multiple myeloma.

6.2 Phase I Portion

To determine the MTD of the combination of thalidomide, lenalidomide and dexamethasone (LTD), with 4 dose levels planned. Dosing will start at doses of LTD that are intermediate intensity because of overlapping side effect profile of lenalidomide and thalidomide to determine the MTD and maximize the overall response rate of the regimen.

Table 6-1 Dose Levels to be studied

Dose Level	Assigned Therapy
Level -1	15 mg Lenalidomide daily on days 1-21 followed by 7-day rest every 28 days 50 mg Thalidomide daily 40 mg dexamethasone *
Level 1	15 mg Lenalidomide daily on days 1-21 followed by 7-day rest every 28 days 100 mg Thalidomide daily 40 mg dexamethasone *
Level 2	25 mg Lenalidomide daily on days 1-21 followed by 7-day rest every 28 days 100 mg Thalidomide daily 40 mg dexamethasone *
Level 3	25 mg Lenalidomide daily on days 1-21 followed by 7-day rest every 28 days 200 mg Thalidomide daily 40 mg dexamethasone

* Dexamethasone dosing for cycle 1-2: 40 mg days 1-4, 9-12, and 17-20; all subsequent cycles: 40 mg days 1,8, 15, 21

Dose Escalation

The first cohort of three patients enrolled into the study will receive dose level 1. A full safety evaluation will be conducted when these subjects have completed one cycle (28 days) of combination therapy.

Definition of DLT

A DLT will be defined as follows:

- Hematologic dose-limiting toxicity will be defined as either Grade 4 neutropenia lasting for ≥ 7 days in duration, any Grade 4 thrombocytopenia, or any Grade 5 hematologic toxicity. At least three patients in each cohort must be evaluable for hematologic toxicity.
- Non-hematologic dose-limiting toxicity will be defined as any Grade 3, 4 or 5 non-hematologic toxicity, with the specific exception of:
 - Isolated Grade 3 elevation of liver function tests (LFTs) without associated clinical symptoms, lasting for ≤ 7 days in duration.
 - Isolated Grade 3 elevation of amylase without associated clinical symptoms
 - Grade 3 hypocalcemia, hypokalemia, hypomagnesemia, hyponatremia, or hypophosphatemia which responds to medical intervention.

Definition of Maximum Tolerated Dose:

The MTD of the combination of lenalidomide, thalidomide and dexamethasone in multiple myeloma subjects shall be defined at the end of the trial, the dose with the smallest absolute value of (*posterior mean of pi-pT*) among all the tried doses *i* for which $T_i=0$ will be selected as the MTD.

The dose will be escalated either until an MTD is identified or the maximum planned dose is achieved.

6.3 Phase II

Patients will be enrolled in the phase II portion of this study at the dosing regimen established in the phase 1 portion. Patients will be assessed for response each cycle of therapy.

An additional cohort of 10 patients with myeloma refractory to lenalidomide will be enrolled. This cohort of patients will be treated at the MTD regimen, with lenalidomide 25 mg po days 1-21 on a 28 day cycles and thalidomide 100 mg po daily. The dose of dexamethasone will be 40 mg po weekly.

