6.7 On-study evaluations

Subjects who meet eligibility criteria will be enrolled into the study, and will be assigned a patient number.

Cycle one patients will be followed weekly on Cycle 1, Day 8, 15, 22 (+/- 3 days):

- Clinical laboratory tests: Blood chemistry [sodium, potassium, chloride, CO₂, calcium, magnesium, phosphorus, blood urea nitrogen (BUN), creatinine, glucose, albumin, total protein, alkaline phosphatase, total bilirubin, aspartate transaminase (SGOT/AST), glutamic pyruvic transaminase (SGPT/ALT), lactate dehydrogenase (LDH)
- Hematology: hemoglobin, hematocrit, white blood cell (WBC) count and differential, and platelet count.
- Symptom directed physical examination/vitals

Day 1+/- 7 days of each cycle of therapy (starting with cycle 2):

- Standard myeloma restaging studies including SPEP, UPEP, Free Light Chain measurements (SIFE, UIFE and Bone Marrow biopsy will be done at time of suspected complete remission to document complete remission). MRI and skeletal surveys will be done as clinically indicated to follow the disease.
- Directed neurologic examination will be performed, and questioning for symptoms of paresthesia and numbness.
- Physical Examination
- Clinical laboratory tests: Blood chemistry [sodium, potassium, chloride, CO₂, calcium, magnesium, phosphorus, blood urea nitrogen (BUN), creatinine, glucose, albumin, total protein, alkaline phosphatase, total bilirubin, aspartate transaminase (SGOT/AST), glutamic pyruvic transaminase (SGPT/ALT), lactate dehydrogenase (LDH)
- Hematology: hemoglobin, hematocrit, white blood cell (WBC) count and differential, and platelet count.
- 12 lead EKG
- Patients will be evaluated for AEs at each visit with the NCI CTCAE v3.0 used as a guide for the grading of severity.
- Multiple-symptom assessment tool (also known as the MDASI).
- Blood sample for Serum Cytokines every even cycle.

An unscheduled visit can occur at any time during the study. Source must be maintained for these unscheduled visits.

Multiple-symptom assessment tool (Also known as MDASI)

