7.0 Statistical Consideration

This is an open label, phase I/II clinical trial to evaluate the safety and efficacy of lenalidomide, thalidomide, and dexamethasone in patients with relapsed/refractory multiple myeloma. The maximum number of patients that will be recruited for the study is 64.

Phase I design:

The objective of the phase I portion is to determine the maximum tolerated dose (MTD) of the combination regimen of lenalidomide, thalidomide, and dexamethasone. There are four predefined dose levels for lenalidomide, thalidomide, and dexamethasone, and the first cohort of patients will be treated at the second dose (Dose Level 1).

Dose Level	Assigned Therapy
Level -1	15 mg Lenalidomide daily on days 1-21 followed by 7-day rest every 28 days 50 mg Thalidomide daily 40 mg dexamethasone *
Level 1	15 mg Lenalidomide daily on days 1-21 followed by 7-day rest every 28 days 100 mg Thalidomide daily 40 mg dexamethasone *
Level 2	25 mg Lenalidomide daily on days 1-21 followed by 7-day rest every 28 days 100 mg Thalidomide daily 40 mg dexamethasone *
Level 3	25 mg Lenalidomide daily on days 1-21 followed by 7-day rest every 28 days 200 mg Thalidomide daily 40 mg dexamethasone

Dose limiting toxicity (DLT) is defined as in the treatment plan. To find the MTD, a statistical design based on a Bayesian model described in Ji, Li, and Bekele (2006) will be used. The details of the design are described below.

Let p_i denote the toxicity probabilities for dose $i=1, 2, 3, \text{ and } 4$. The goal is to accurately estimate the probability of toxicity at the current tried dose level. Assuming a vague independent beta prior $B(0.005, 0.005)$ for each p_i , with observed data (n_i, x_i) , where n_i represents the number of patients treated at current dose and x_i represents the number of patients experienced DLTs, the posterior of p_i follows an independent $B(0.005 + x_i, 0.005 + n_i - x_i)$ for $i=1, 2, 3, \text{ and } 4$. Let

$$T_i = 1\{P(p_i > p_T \mid \text{data}) > \xi\}$$

We define the posterior probabilities of three possible actions as

$$q(D, i) = P(p_i > p_T + K_1 \sigma_i \mid \text{data})$$

$$q(S, i) = P(p_T - K_2 \sigma_i \leq p_i \leq p_T + K_1 \sigma_i \mid \text{data})$$

$$q(E, i) = P(p_i < p_T - K_2 \sigma_i \mid \text{data}) * (1 - T_i)$$

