where D represents the action of de-escalating to next lower level, S represents staying at current dose and E represents escalating to next higher level, and σ_i is the posterior deviation of p_i . The dose-assignment rule B_i is defined as $B_i^{(e)} = \arg \max_{m \in \{D, S, E\}} q(m, i)$.

[figure not shown]
Based on dose-assignment rule $B_i^{(e)}$, a dose-finding algorithm is proposed as follows:

- 1) Suppose that Dose 1 is a dose that has been tried previously. If $T_i = 1$, terminate the trial due to excessive toxicity. Otherwise, terminate the trial when the maximum sample size is reached.
- 2) At current tried dose i , the decision to select the dose for next cohort are among $\{(i-1), i, (i+1)\}$ based on the assignment rule. There are two exceptions, however: if $i=1$, the next available doses are $\{1, 2\}$; if $i=4$, the next available doses are $\{3, 4\}$.
- 3) At the end of the trial, the dose with the smallest absolute value of (*posterior mean of $p_i - p_T$*) among all the tried doses i for which $T_i=0$ will be selected as the MTD.

Let $\xi = 0.95$, $K_1=1$ and $K_2=1.5$. Starting at Dose Level 1 (the second dose), the trial will enrol patients in a cohort size of three. The maximum sample size is 18 and the MTD has a probability of toxicity $p_T=0.4$. Table 1 presents the monitoring rules for each dose and Table 2 presents the operating characteristics of the proposed design under six toxicity scenarios. When MTD is among the doses studied (Scenarios 1, 2, and 3), this dose will be selected with the highest probability and the number of patients treated at this dose will be the largest among all doses. If all the Dose levels turn out to be too toxic (Scenario 6), the chances of these doses being selected are very low and most of the few patients treated will be at the lowest dose level. On the other hand, if all the Dose levels are below the MTD (Scenario 5), the highest dose will be chosen with the highest probability and most patients will be treated at the highest dose.

Table 1. Dose-finding trail-monitoring chart

		Number of patients treated at current dose																	
		1	2	3	4	5	6	7	8	9	10	11	12	13	14	15	16	17	18
Number of toxicities	0	E	E	E	E	E	E	E	E	E	E	E	E	E	E	E	E	E	E
	1	D U	S	S	S	E	E	E	E	E	E	E	E	E	E	E	E	E	E
	2		D U	S	S	S	S	S	S	E	E	E	E	E	E	E	E	E	E
	3			D U	D	S	S	S	S	S	S	S	S	E	E	E	E	E	E
	4				D U	D	D	S	S	S	S	S	S	S	S	S	E	E	E
	5					D U	D	D	D	D	S	S	S	S	S	S	S	S	S
	6						D U	D	D	D	D	D	S	S	S	S	S	S	S

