	7							D U	D	D	D	D	D	D	S	S	S	S	S
	8								D U	D	D	D	D	D	D	D	S	S	S
	9									D U	D	D	D	D	D	D	D	D	S
	10										D U	D	D	D	D	D	D	D	D
	11											D U	D	D	D	D	D	D	D
	12												D U	D	D	D	D	D	D
	13													D U	D	D	D	D	D
	14														D U	D	D	D	D
	15															D U	D	D	D
	16																D U	D	D
	17																	D U	D
	18																		D U

E = Escalate to next higher dose

S = Stay at current dose

D = De-escalate to next lower dose

U = Current dose is unacceptable

Table 2. Operating characteristics

Scenario		Dose -1	Dose 1	Dose 2	Dose 3	Total # of Pts	Overall Toxicity
1	Toxicity Rate	0.4	0.55	0.65	0.65	17.568	0.535121
	Chance Selected	0.507	0.313	0.08	0.015		
	# of Pts Treated	5.799	6.069	5.322	0.378		
2	Toxicity Rate	0.05	0.1	0.4	0.6	18	0.366222
	Chance Selected	0.002	0.17	0.703	0.125		
	# of Pts Treated	0.432	3.321	11.718	2.529		
3	Toxicity Rate	0.05	0.1	0.15	0.4	18	0.287222
	Chance Selected	0	0.003	0.232	0.765		
	# of Pts Treated	0.012	0.48	7.164	10.344		
4	Toxicity Rate	0.2	0.35	0.55	0.6	17.979	0.435675
	Chance Selected	0.12	0.53	0.322	0.025		
	# of Pts Treated	2.073	7.074	7.941	0.891		
5	Toxicity Rate	0.05	0.1	0.15	0.2	18	0.184056
	Chance Selected	0	0.005	0.114	0.881		
	# of Pts Treated	0.03	0.315	5.991	11.664		
6	Toxicity Rate	0.5	0.6	0.65	0.7	17.16	0.574242
	Chance Selected	0.492	0.233	0.078	0.004		
	# of Pts Treated	6.216	5.283	5.388	0.273		

Phase II design:

During the phase II portion of the study, patients will be treated with lenalidomide, thalidomide, and dexamethasone in combination at the MTD established in the phase I portion. Furthermore, the patients treated at the MTD in the phase I portion of the study will be considered the first patients of the phase II portion. It is anticipated that at least 6 patients will be treated at the MTD in the phase I and will be later included in the analysis of the phase II portion.

Response will be assessed after 4 cycles of therapy.

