The overall response and toxicity will be monitored simultaneously using the Bayesian approach of Thall, Simon, Estey (1995, 1996) as extended by Thall and Sung (1998). Historical data on similar patients show an overall response rate (ORR) of 30% and toxicity rate of 30%. However, the information was down-weighted to reflect the same marginal ORR and toxicity rates in 2 patients. Independence was assumed between OR and toxicity. It is expected for the current trial that the three-drug combination will improve the ORR to 50% while the toxicity rate is maintained at 40%. A sample size of 36 ensures that, if the trial is not terminated early, a posterior 90% credibility interval for overall response rate will have width of 0.26 at most, under the assumption of a 50% of ORR. The probabilities of OR and toxicity for the historical data are modeled by beta distributions ($Beta(3, 7)$ and $Beta(3, 7)$, respectively). The prior probabilities of OR and toxicity for the experimental regimen are also modeled by beta distributions ($Beta(0.6, 1.4)$ and $Beta(0.6, 1.4)$, respectively), which have the same a/b (a and b denote the parameters for a $Beta$ distribution) ratio as the beta distributions for the historical data. Denoting the historical probabilities of overall response rate and toxicity rate by $\{p(OR,H), p(TOX,H)\}$, the following decision criteria will be applied:

- 1) Let E correspond to the experimental treatment, stop if $\text{Prob}\{p(OR,H) + \delta_{OR} > p(OR,E) | \text{data}\} > 0.90$, where $\delta_{OR} = 0.20$
- 2) Stop if $\text{Prob}\{p(TOX,H) + \delta_{TOX} < p(TOX,E) | \text{data}\} > 0.85$, where $\delta_{TOX} = 0.10$

Patients will be monitored according to the following stopping boundaries for overall response.

Number of patients evaluated	Recommend stopping if \leq OR observed
12	3
24	7
36	11

At the same time, patients will be monitored according to the following stopping boundaries for toxicity.

Among these number of patients	Recommend stopping if \geq toxicity observed
12	8
24	15
36	22

The operating characteristics are summarized in the following table (based on simulations from 10,000 trials).

True Toxicity Rate	True OR Rate	Prob(stop the trial early)
0.1	0.3	0.654
	0.4	0.296
	0.5	0.086

	0.6	0.016
	0.7	0.002
0.25	0.3	0.655
	0.4	0.298
	0.5	0.089
	0.6	0.019
	0.7	0.005
0.4	0.3	0.677
	0.4	0.343
	0.5	0.147
	0.6	0.082
	0.7	0.068
0.55	0.3	0.795
	0.4	0.583
	0.5	0.225
	0.6	0.417
	0.7	0.409

Analysis Plan

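### The added 10-patient lenalidomide-refractory cohort has no toxicity look or boundary that can act while it is being treated; a gate at 36 and a small cohort rule would supply one cheaply

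*Combined protocol and SAP*

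**What the plan says.** Section 6.3 (Phase II): "An additional cohort of 10 patients with myeloma refractory to lenalidomide will be enrolled". They receive lenalidomide 25 mg on days 1-21, thalidomide 100 mg daily and weekly dexamethasone 40 mg. Section 6.8.2 calls them the last cohort of phase II and starts weekly dexamethasone at cycle 1. Main-cohort patients take 40 mg on 12 days of each of cycles 1 and 2.

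Section 7.0 does not mention the cohort. It gives an overall ceiling: "The maximum number of patients that will be recruited for the study is 64". Phase II is sized at 36, and the plan expects that "the three-drug combination will improve the ORR to 50% while the toxicity rate is maintained at 40"%. For safety it says: "At the same time, patients will be monitored according to the following stopping boundaries for toxicity", followed by rows at 12, 24 and 36 only. Toxicity criterion 2, from which those rows come, refers to the experimental treatment without an upper sample size.

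The other controls are:
- retreatment criteria (6.3.3);
- holds and reductions at the physician's discretion (6.3.1, 6.3.2, 6.11);
- discontinuation on the investigator's judgement (6.12);
- weekly meetings led by the principal investigator (8.0);
- serious adverse event reporting to the drug supplier, the IRB and the FDA (9.4.1 to 9.4.3).

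**The concern.** The sponsor gave the main phase II patients a numerical toxicity stop. It then added a separately defined population on a different dexamethasone schedule and set no number for it. If the main cohort passes and toxicity then appears in these ten, the weekly meeting has no agreed count at which to recommend closing the cohort. Nor does the plan say whether the result at 36 decides if the cohort opens. Up to ten patients' exposure is at stake; the primary response analysis is not.

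**Working it through.** **Is the cohort outside the 36?** The text calls it additional and last, and section 6.1 gives an enrolment range of 54-64, whose width (64 - 54 = 10) equals the cohort size. Phase I has a ceiling: "The maximum sample size is 18 and the MTD has a probability of toxicity" of 0.4. So 18 + 36 = 54, and 54 + 10 = 64. This is only a maximum, because phase I patients at the MTD "will be considered the first patients of the phase II portion". With the six anticipated there, distinct patients number 18 + 36 - 6 = 48, or 58 with the cohort. The reading is reasonable but inferred.

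**Reproducing the plan's boundaries.** Inputs from section 7.0: historical toxicity pH ~ Beta(3, 7); prior for the regimen Beta(0.6, 1.4); margin 0.10; cut-off 0.85. With x toxicities in n patients, pE ~ Beta(0.6 + x, 1.4 + n - x), and the rule stops if P(pE > pH + 0.10) > 0.85. Numerical integration gives:

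| n | At the boundary | One fewer |
|---|---|---|
| 12 | 8: 0.869 | 7: 0.776 |
| 24 | 15: 0.877 | 14: 0.829 |
| 36 | 22: 0.881 | 21: 0.849 |

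All three printed boundaries reproduce.

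**Pooling to 46.** 26/46 gives 0.835 and 27/46 gives 0.862, so the boundary is 27. With 14/36 in the main group (about 40%), even 10/10 in the cohort totals 24 and does not stop. The main group would need at least 17, since 17 + 10 = 27. If the main cohort has 40% toxicity and passes (probability 0.931), the pooled look fires with probability 0.012, 0.038 or 0.072 at cohort toxicity 0.55, 0.70 or 0.80, and only after all ten are treated.

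**Gate at 36.** Exact binomial recursion for the main cohort:

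| True toxicity | Stopped at 12 or 24 | Stopped at 12, 24 or 36 |
|---|---|---|
| 0.40 | 0.066 | 0.069 |
| 0.55 | 0.408 | 0.462 |
| 0.60 | 0.587 | 0.666 |

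A stated gate at 36 therefore adds 0.054 at 55% toxicity and almost nothing at 40%.

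**Criterion 2 on the cohort alone.** 3/3 gives 0.904 (2/3: 0.682) and 5/6 gives 0.917 (4/6: 0.790). The rule is therefore to stop at 3 of 3 or 5 of 6. P(stop at 3) = p³. A first stop at 6 needs 2 of the first 3 and then 3 of 3: 3p²(1 - p) × p³.

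| True toxicity p | Stop at 3 | Stop at 6 | Total |
|---|---|---|---|
| 0.40 | 0.064 | 0.018 | 0.082 |
| 0.55 | 0.166 | 0.068 | 0.234 |
| 0.60 | 0.216 | 0.093 | 0.309 |
| 0.70 | 0.343 | 0.151 | 0.494 |

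**Patients spared.** Accrual is not given, so let e be the number of further patients started before each look (an assumption, shown as a range). Spared = P(stop at 3) × max(0, 7 - e) + P(stop at 6) × max(0, 4 - e).

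| e | p = 0.55 | p = 0.70 |
|---|---|---|
| 0 | 1.44 | 3.01 |
| 1 | 1.20 | 2.51 |
| 2 | 0.97 | 2.02 |
| 4 | 0.50 | 1.03 |
| 7 or more | 0 | 0 |

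At an assumed two starts per 28 days, a 28-day wait gives e = 2. A four-cycle (112-day) wait gives e = 8, and the rule spares nobody.

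**Single look at 6 (5/6).** Stopping is 0.041, 0.164 and 0.420 at 0.40, 0.55 and 0.70. With e = 0 it spares 4 × 0.164 = 0.65 patients at 0.55 and 4 × 0.420 = 1.68 at 0.70.

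**The case against.** A reader might infer that no toxicity rule of any kind reaches this cohort. The documents do not support that: criterion 2 is general and these are phase II patients. What is missing is a look that can act in time. A reader might also infer that the plan commits to treating all ten whatever happens. It does not: individual controls and serious adverse event reporting remain, the latter bringing in people beyond the investigator. Nor do the documents suggest more toxicity here. Dexamethasone is 4 × 40 = 160 mg per cycle, against 12 × 40 = 480 mg in main-cohort cycles 1 and 2.

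The gate is arguably implied already, since a crossed boundary at 36 recommends stopping and this cohort is described as last. That depends on enrolment order, so (a) in the fix is mainly a clarification.

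Two objections to the cohort rule carry weight. First, a strict 28-day window would miss late harm. Section 1.3.5 reports lenalidomide dose modifications for myelosuppression beyond day 28, and section 1.3.3 says thalidomide neuropathy usually follows months of use. Second, section 7.0 defines neither phase II toxicity nor its window. That the phase I target (0.40) equals the expected phase II rate (40%) does not show that DLTs and the Beta(3, 7) rate count the same events.

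The rule is also weak. It misses 77% of cohorts at 55% toxicity (1 - 0.234) and 51% at 70% (1 - 0.494), and most of its stops at 40% come from the first three patients (0.064 of 0.082). It is still better than a pooled look that fires after treatment is complete.

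**Conclusion.** The point holds as a cheap improvement of modest severity: no toxicity look or boundary can act while the ten are being treated. A cohort rule would stop with probability 0.08, 0.23 and 0.49 at true toxicity 0.40, 0.55 and 0.70, sparing 0 to 1.4 patients at 0.55 and 0 to 3.0 at 0.70. The upper ends require that no further patient starts before each look.

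This rests on three assumptions: the ten lie outside the 36; DLTs are on the same scale as the historical toxicity rate; and accrual is slow enough for a look to matter. True toxicity here means the chance of a counted event by the time of review.

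**What to change.** In section 7.0:

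(a) State that the lenalidomide-refractory cohort opens only if the 36-patient toxicity boundary (22) has not been crossed.

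(b) Apply criterion 2 to this cohort alone, with the same prior, margin and cut-off: recommend stopping the cohort at 3 or more toxicities in the first 3 patients or 5 or more in the first 6. Review at the existing weekly meeting once those patients have completed cycle 1. Count toxicities meeting the section 6.2 DLT definition, including any later ones already seen in enrolled patients at the time of review.

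(c) State the phase II toxicity definition and window, so that the calibration can be checked.

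The timing matches phase I, where "A full safety evaluation will be conducted when these subjects have completed one cycle (28 days) of combination therapy", and the visits already exist: "Cycle one patients will be followed weekly on Cycle 1, Day 8, 15, 22 (+/- 3 days"). Looks at 3 and 6 are needed because a cohort of ten never reaches the first look at 12. Pausing accrual at each look is optional and moves the saving towards its upper end.

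The cost is a few lines of text, using existing staff and visits. There is an 8% chance of stopping the cohort at the accepted 40% toxicity, against 7% for the main rule. If that is too high, the single look at six cuts it to 4%, with less protection. The gate may delay opening until the 36th patient is evaluable, about 28 days if toxicity is read in cycle 1 (an assumption).
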